## **SYNOPSIS**

Title: Prospective Study Comparing Brand and Generic Immunosuppression on Transplant Outcomes, Adherence, & Immune Response in Kidney Transplant Recipients

Estimated Number of Study Centers: 4

Study Phase: 4

Research Hypothesis: Kidney transplant recipients who received generic tacrolimus will have outcomes that are not inferior to those who received brand tacrolimus during the one-year study period.

Primary Objective: To analyze the effects of use of brand tacrolimus versus generic tacrolimus, on a composite event of either acute rejection, or graft failure, or subject death.

- Acute Rejection will be defined according to the Banff 2007 classification
- Graft failure will be defined as a return to dialysis, re-transplant, or death

Secondary Objectives: To analyze the effects of use of brand tacrolimus versus generic tacrolimus on acute rejection, graft failure, subject death, individual rates of infection, immunologic markers of immunosuppression, subject compliance, and subject acceptance.

Study Design: Phase IV prospective, randomized, open labeled, multicenter, 2-group, parallel, observational study.

Duration of Study: 1 year

Number of Subjects: 200. Study Population: Kidney recipients; no more than 14 days after transplantation and prior to discharge.

Reference Product, Dose, Mode of Administration, and Duration of Treatment: Brand tacrolimus, dosing to be determined by the treating physician and recorded in subjects' study file, to be administered orally (tacrolimus level to be 4-11ng/dL) for a duration of 1 year.

Test Product, Dose, Mode of Administration, and Duration of Treatment: Generic tacrolimus, dosing to be determined by the treating physician and recorded in subjects' study file, to be administered orally (tacrolimus level to be 4-11ng/dL) for a duration of 1 year.

Criteria for Evaluation:

Primary outcome measures:

Time to a composite event, which is defined as the time to first occurrence of acute rejection, failure, death.

Secondary Outcome Measures:

- Graft rejection at 1 year after transplant
- Graft failure at 1 year after transplant
- Incidence of infectious episodes at 1 year after transplant
- Incidence of malignancy at 1 year after transplant
- Death or loss-to-follow-up at 1 year after transplant
- Adherence with medication regimen

Statistical methods: The primary efficacy endpoint will be analyzed as time-to-event, with follow-up time measured in days from the date of transplant to the date of composite endpoint. Statistical testing of time until composite event will be done for the intention-to-treat population, with adjustment for center (Cox regression). Data will also be collected on subjects who are lost to follow up. The intention-to-treat population will consist of all randomized patients who received at least 1 dose of investigational drug (brand or generic tacrolimus).

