### 3.5 Data Safety and Monitoring Board Review Responsibilities

A Data and Safety Monitoring Board (DSMB) will be convened for only Phase 1 of the study trial, to act in an advisory capacity to monitor participant safety, evaluate the progress of the study, review procedures for maintaining the confidentiality of data, and review the quality of data collection, management, and analyses. The DSMB will include 3 people with no interest or participation in research activities associated with this trial. DSMB members will not have any direct involvement with the study investigators or intervention. Each DSMB member will sign a Conflict of Interest Statement which includes current affiliations, if any, with pharmaceutical and biotechnology companies (e.g., stockholder, consultant), and any other relationships that could be perceived as a conflict of interest related to the study objectives. Members of the Board will include experts in subject education, cultural tailoring, randomized controlled trials, and kidney transplantation.

The Board will be instructed to review the study and its educational components to look for any component of the design or education that could result in harm of study participants. Data will be presented in a blinded manner during the open sessions of the DSMB. At DSMB meetings, data and discussion are confidential. There will be no DSMB for Phase 2 of the study. This is because the Phase 2 part of the study is open label, where standard of care procedures are being performed. There will be no use of any investigational drug. The Principal investigator will continue to monitor participant safety per study site standard of care guidelines.

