## 6.2 Study Therapy

**6.2.1 Clinical Sites:** Kidney recipients will be enrolled at UCLA, UCSD, UCI, UC Davis Medical Centers. Mechanistic studies will be performed utilizing specimens collected from all sites. Adherence will be measured with daily medication diaries, and with the coefficient of variation of tacrolimus in subjects' blood.

**6.2.2 References and comparator arms:** During phase 1 of study, following consent and randomization, the control group were prescribed brand tacrolimus and the comparator group was prescribed generic tacrolimus. The study drugs were prescribed upon discharge, but no later than 14 days after transplant. Subjects continued to receive study drug for up to one year post-transplant. During phase 2 of study, generic tacrolimus will only be prescribed as part of their regular care upon discharge but no later than 14 days after transplant.

**6.2.3 Provision of investigational drugs:** We anticipate that brand and generic tacrolimus will be provided for the entire study period for Phase 1 of the study. Generic tacrolimus will be obtained by the subject through their insurance for Phase 2 only. (See letters from Astellas - Appendix 5)

**6.2.4 Number of subjects and sample size justification:** We plan to enroll a total of 200 subjects between the four sites. Of the 200 kidney recipients at least 20 will be African American recipients. 40 randomized subjects will be on Brand and 160 subjects will be on generic.

**6.2.5 Eligible Subjects:** In Phase 1, eligible subjects will be initially randomized using a ratio of 2:1 (Brand:Generic) until 40 subjects have been enrolled into the brand medication arm (Arm 1) and 20 have been enrolled into the generic medication arm (Arm 2). In Phase 2, 140 additional eligible subjects will be enrolled without randomization onto generic tacrolimus only as part of their regular care. All subjects will be followed for 1-year post-transplant. (A split-phase randomization process is necessary due to a limited supply and narrow expiration-time window associated with the Brand medication product.)

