**6.2.6 Screening, recruiting and eligibility:** All Kidney recipients that are 1) less than 30 days pre-transplantation or 2) up to 14 days post-transplantation, but prior to discharge, who are deemed a candidate for a tacrolimus immunosuppression regimens and meet the inclusion and exclusion criteria above, are eligible for the study. They will be invited to participate and given written informed consent for enrollment. We will attempt to enroll all subjects in a 12-month time period.

**6.2.7 Study enrollment and randomization:** This randomized, prospective, open-labeled, 2-group, parallel observational study will enroll a total of 200 subjects across 4 clinical sites. During phase 1 of the study, randomization was done after the informed consent process, using a block system pre-generated by a computer and stratified by site, ethnic group, and age cohort. During phase 2 of the study, no randomization will occur, and all subjects will be placed onto standard of care generic tacrolimus.

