### Table 5 - Study Schedule

|   | Baseline | 1 mo. | 2 mo. | 3 mo. | 6 mo. | 9 mo. | 12 mo. |
|---|----------|-------|-------|-------|-------|-------|--------|
| Obtain informed consent                     | x        |       |       |       |       |       |        |
| Confirm inclusion/exclusion                 | x        |       |       |       |       |       |        |
| Review medical history                      | x        | x     | x     | x     | x     | x     | x      |
| Review physical exam                        | x        | x     | x     | x     | x     | x     | x      |
| Review concomitant medications              | x        | x     | x     | x     | x     | x     | x      |
| AE monitoring (Safety labs)                 |          | x     | x     | x     | x     | x     | x      |
| Review of labs                              | x        | x     | x     | x     | x     | x     | x      |
| Randomization *                             | x        |       |       |       |       |       |        |
| Tacrolimus dispensation (if applicable)     | x        | x     | x     | x     | x     | x     |        |
| Tacrolimus level from routine clinical labs |          | x     | x     | x     | x     | x     | x      |
| Review dosing diary                         |          | x     | x     | x     | x     | x     | x      |

\*Randomization for Phase 1 only, no randomization will occur during Phase 2 as all subjects will be placed on generic drug.

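### The primary test is assigned to an ITT set of randomized patients, but only 60 of the 200 subjects behind its event count and power are randomized

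*Combined protocol and SAP*

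**What the plan says.** The Synopsis assigns the primary test: "Statistical testing of time until composite event will be done for the intention-to-treat population, with adjustment for center (Cox regression". It then gives the only definition of that population in the document: "The intention-to-treat population will consist of all randomized patients who received at least 1 dose of investigational drug (brand or generic tacrolimus". Section 4.2 repeats the assignment to ITT. Section 3.4 lists an ITT basis among its power assumptions, comparing Arm 2 with Arm 1.

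Section 6.2.5 randomizes 2:1 in Phase 1 until "40 subjects have been enrolled into the brand medication arm (Arm 1) and 20 have been enrolled into the generic medication arm (Arm 2". After that, "140 additional eligible subjects will be enrolled without randomization onto generic tacrolimus only as part of their regular care". Section 6.2.7 agrees: "During phase 2 of the study, no randomization will occur, and all subjects will be placed onto standard of care generic tacrolimus". So does the footnote to Table 5: "no randomization will occur during Phase 2 as all subjects will be placed on generic drug".

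Section 3.4 bases its calculation on 200 subjects split 50 brand and 150 generic, with 25 events (6 and 19) and more than 80% power against a margin HR of 3.54. Sections 6.2.4 and 6.2.8 plan 40 and 160 instead.

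Three wording conflicts belong to the same problem:
- The Synopsis, 1.2, 3.1, 6.2.7 and 6.2.8 describe the study as randomized without limiting this to Phase 1.
- Section 3.1 starts Phase 2 after 40 Phase 1 subjects, while 6.2.5 implies 60.
- Section 3.5 says of Phase 2 "There will be no use of any investigational drug", while the Synopsis counts generic tacrolimus as investigational drug.

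**The concern.** The plan does not say consistently who is in its primary test. As defined, ITT leaves out 140 of 200 subjects (70%) and 140 of 160 generic subjects (87.5%). No section extends ITT to Phase 2 or names another set for the primary test.

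Each reading has its own cost. If the definition is followed, the test does not have the power that 3.4 states. If all 200 are analysed, the ITT label claims a protection by randomization that most of the generic arm does not have. Phase 1 was randomized "using a block system pre-generated by a computer and stratified by site, ethnic group, and age cohort", but the primary model adjusts only for center. Brand subjects enter only in Phase 1 and most generic subjects only in Phase 2, so the comparison is largely non-concurrent. Drug supply also differs: 6.2.3 has the study providing drug in Phase 1, while Phase 2 subjects obtain it through insurance. If the set is left open, it could be chosen after results are known.

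**Working it through.** **Inputs.** 13% with an event by one year, margin HR 3.54 and true HR 1 (3.4); 5% dropout (Table 1); one-sided 5% through the upper bound of a 90% CI (4.2); one year of follow-up per subject and the Phase 1 and Phase 2 numbers (6.2.5). Taking dropout as exponential is my assumption.

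**Event probability.** Event hazard = -ln(0.87) = 0.1393 per year. Dropout hazard = -ln(0.95) = 0.0513 per year. P(event observed) = 0.1393/(0.1393 + 0.0513) × (1 - 0.87 × 0.95) = 0.1268.

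**The plan's own figures first.** 200 × 0.1268 = 25.4 events, split 6.3 and 19.0, against the stated 25 (6 and 19). For the margin, 0.87^3.54 = 0.61, which is 26 points below 87%. Power at 25 events split 1:3 is 86% one-sided, in line with more than 80%. On its own inputs the calculation reproduces.

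**Formulas.** Normal: power = Φ(ln 3.54/SE - 1.645), with SE = √(1/e_brand + 1/e_generic) and ln 3.54 = 1.264. Log-rank variant: power = Φ(√(D·p_brand·p_generic) × (3.54 - 1)/√3.54 - 1.645), where D is total events, p the arm shares, and 2.54/√3.54 = 1.350.

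| Set | Brand / generic | Expected events | SE | Normal | Log-rank |
|---|---|---|---|---|---|
| Randomized, as defined | 40 / 20 | 5.07 + 2.54 = 7.6 | 0.769 | 50% | 54% |
| All enrolled, as planned | 40 / 160 | 5.07 + 20.29 = 25.4 | 0.496 | 82% | 86% |
| As computed in 3.4 | 50 / 150 | 6.34 + 19.02 = 25.4 | 0.459 | 87% | 90% |

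Example for 40/20: 1.264/0.769 - 1.645 ≈ 0, so power is 50%. Without dropout the 40/20 figures are 7.8 events and 51% and 55%. The two candidate sets differ by 25.4 - 7.6 = 17.8 events. If Phase 1 held only 40 subjects at 2:1, as 3.1 could be read, expected events would be 5.1 and power 38% (normal formula).

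**Simulation check.** With 5 to 6 brand events the formulas are approximate, and 4.2 does not name the type of interval. Simulated Cox fits of the 90% CI rule, with and without center terms, gave:
- 40/20: 42-45% (Wald), 51-53% (likelihood ratio and score).
- 40/160: 71-74% (Wald), 67-68% (likelihood ratio), 73% (score).
- 50/150: 78-79% (Wald), 74-75% (likelihood ratio), 79% (score).

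Wald runs with no events in one arm (about 7% at 40/20) count as not passing. The formulas are optimistic at all three splits. This comes from the few brand events, not from the ITT mismatch.

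**Illustration for 40/160, an assumption and not a document figure.** If the 140 non-randomized subjects had a baseline hazard 10%, 20%, 30% or 50% lower than the randomized ones, the chance of passing at a true HR of 3.54 would be about 9%, 12%, 18% or 33-35%, against about 6% with no difference. If their hazard were 25% or 50% higher, simulated power at HR 1 would fall from 72% to 64% or 55%. The documents give neither the size nor the direction of any difference.

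**The case against.** The strongest reply is that the plan means all 200. Section 3.4 sizes the test on 200 subjects and compares Arm 2 with Arm 1, 6.2.4 plans 40 and 160, and 6.2.8 gives Arm 2 as n=160. On that reading the ITT sentence is a leftover from a fully randomized design, and more than 80% power survives by formula. This stands as the likelier intent. A reader might infer that the trial's power is really about 50%; the documents do not support that as the intended design. A reader might also infer that the calculation in 3.4 is wrong, but it reproduces on its own inputs. The fault is that it describes a different population from the one defined.

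A second reply is that 4.2 already plans Cox models with age and race covariates. It does, but as exploratory analyses not tied to the primary test.

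A third tempting reading is that Phase 2 subjects picked generic over brand. Section 3.1 does say they chose generic, but it identifies this as the standard of care under their insurance. Phase 2 offers no brand arm, and 6.2.5 attributes the split to limited brand supply and expiry. The documents therefore show non-randomized, later enrolment, not a choice between study arms and not a demonstrated bias. Section 6.2.6 also aims to enroll everyone within 12 months, which would limit the gap between phases.

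**Conclusion.** The inconsistency is real and concerns the primary test. The 200 subjects, 25 events and more than 80% power in 3.4 do not belong to the ITT population that the Synopsis defines. Taken literally, that population has about 7.6 expected events and 50-54% power by formula (42-45% when the Wald rule is simulated). Taken as probably intended, the set has about 25.4 events and 82-86% by formula, 4 to 5 points below the same formulas at 50/150, and it is not an ITT comparison.

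The figures rest on the plan's 13%, 5% dropout treated as exponential, true HR 1, and the 60 randomized subjects of 6.2.5. The mismatch itself depends on none of these assumptions; it follows from the text alone.

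**What to change.** In the Synopsis, 3.4 and 4.2, define two sets:
1. The randomized Phase 1 set: subjects randomized in Phase 1 who took at least one dose of brand or generic tacrolimus.
2. The all-enrolled treated cohort: Phase 1 and Phase 2 subjects with at least one such dose (planned 40 + 160), labelled as a mostly non-randomized, largely non-concurrent comparison and not as ITT.

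Naming the two products instead of investigational drug removes the conflict with 3.5.

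The sponsor names, before analysis, which set carries the primary test, and reports the HR with 90% CI in both. The 3.54 margin and the decision rule stay as they are. If set 2 is primary, promote the age and race/ethnicity Cox model from exploratory in 4.2 to a named sensitivity analysis of the primary test. State that it does not remove confounding by enrolment period, drug supply or other factors.

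Restate 3.4 at the allocation of the chosen set: 40/160 (25.4 events, 82-86% by formula) or 40/20 (7.6 events, 50-54% by formula), in place of 50/150 and the 6 and 19 events. Add that with so few brand events the formula is optimistic. Describe only Phase 1 as randomized in the Synopsis, 1.2, 3.1, 6.2.7 and 6.2.8, and reconcile the Phase 1 size between 3.1 and 6.2.5.

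The cost is an amendment with IRB review (10.1), one extra results table and a less favourable stated power. No new patients or data are needed. A result from set 2 could not be presented as randomized ITT.

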## **1 INTRODUCTION**

### **1.1 Research Hypothesis**

Primary hypothesis:

Kidney transplant recipients who received generic tacrolimus will have outcomes that are not inferior to those who received brand tacrolimus during the one-year study period.

### **1.2 Study Rationale**

As the patents for brand-name immunosuppressive medications expire, there is increasing interest in using generic immunosuppressive drugs. However, despite pharmacokinetic studies showing bioequivalence, questions remain regarding the clinical impact of use of generic immunosuppression. The most important immunosuppressive agent in the modern transplant era is arguably tacrolimus, a calcineurin-inhibitor with a narrow therapeutic index. This study seeks to answer the question regarding the clinical impact of generic tacrolimus use as measured primarily by acute rejection, loss of graft function, and subject death through a randomized trial of 2 parallel groups: Brand tacrolimus versus Generic tacrolimus. Given that kidney transplantation is the most commonly performed transplant with well-defined measures of rejection and graft failure, this organ will be studied in a four-center study designed to accrue the target number of transplant recipients within the 12-month study period.

### **1.3 Rationale for Dosing**

Because dosing and target tacrolimus levels vary and require customization to subject circumstance, including rejection risk and history of infection, dosing will be decided by each subject's treating physician to approximate a real-world dosing scenario. Please see protocol guidelines for trough level in Section 6.2 study therapy.

### **1.4 Risks and Benefits**

Given that both brand and generic tacrolimus are FDA-approved for use for prevention of rejection after organ transplantation, it is anticipated that trial enrollment will not significantly increase risk for adverse outcomes. Subjects will be monitored closely for adverse events. In addition, in pursuing this study, if increased risk for rejection is found in subjects receiving generic or combination treatment, this information can be used to benefit future transplant recipients.

#### **1.4.1 Overall Risks**

All of the medicines used for prevention of rejection can cause unwanted side effects. Side effects may be experienced early or late following a transplant and may be short or long lasting. The study drugs and procedures may have risks and may cause discomfort. The subject must report to the study staff any side effects or symptoms that he/she experiences.

The potential risks and discomforts related to the subject's participation in this study are listed below. There may be other possible risks and discomforts, which are currently unforeseeable.

## **TACROLIMUS RISKS**

Both generic and Prograf contain the same active ingredient, tacrolimus. The most common side effects of tacrolimus are infection, tremor, hypertension, abnormal kidney function, constipation, diarrhea, nausea, headache, abdominal pain, insomnia (difficulty falling asleep), weakness, urinary tract infection, pain, anemia, swelling of the arms, legs, or feet, decreased magnesium levels in the blood, decreased phosphate levels in the blood, increased lipid levels in the blood, and increased potassium levels in the blood.

Mild increases in potassium levels usually don't cause any symptoms but very increased potassium blood levels can cause heart arrhythmias (abnormal heart rhythm). Heart arrhythmias can sometimes cause the heart to stop beating, which may lead to death. The potassium levels in the blood will be monitored during the study and if the level is elevated it can be treated with medications.

Subjects treated with tacrolimus may develop swelling in the brain called posterior reversible encephalopathy (PRES). Symptoms of PRES are headache, confusion, seizures, high blood pressure, and vision changes. PRES can be treated by lowering the blood pressure and reducing the dose of tacrolimus, with improvement of symptoms.

Taking tacrolimus in any form can cause diabetes, even in persons who never had diabetes before. Symptoms of diabetes can be increased thirst, urination and hunger. Diabetes can be treated with medications including insulin and the condition can improve after the tacrolimus is discontinued. The laboratory testing during the study will watch for this, but subjects will be instructed to report to the study staff if they experience frequent urination or increased thirst or hunger.

All anti-rejection medications may result in infections of the blood, body organs, or tissues. These infections may be caused by various types of bacteria, fungi (yeast and molds), or viruses, especially cytomegalovirus (CMV) and herpes viruses. There is an increased risk for opportunistic infections, including activation of latent viral infections, such as BK virus associated nephropathy and JC virus associated progressive multifocal leukoencephalopathy. These and other types of infections in patients taking immunosuppressive drugs such as tacrolimus can be severe or fatal. The subject should avoid people with contagious diseases (including colds and flu) and keep cuts and scratches clean. Subjects will be instructed to notify their study doctor right away of any new or unusual symptoms that they may experience.

Immunosuppressive medications also increase the risk of cancer, which could be fatal. The most common cancers in a transplant patient are skin cancers and lymphomas or post-transplant lymphoproliferative disorder (PTLD). Lymphoma and PTLN are disorders of the lymphocytes (one of the body's white blood cells that can cause rejection). The development of lymphomas and cancers appears to be related to the overall extent of immunosuppression, rather than to any specific drug. The overall risk of developing any of these cancers is about 1% in transplant patients.

Tacrolimus may cause other side effects. The subject should call the study doctor if he/she has any unusual problems while taking this medication.

